8.4.7 Reporting Events to Participants

All important changes to the risks associated with TTAX01 will be conveyed to study subjects through updated consent forms. Final results of the study will be provided to each Investigator, who will then share individual results with study subjects.

8.4.8 Events of Special Interest

Not applicable.

8.4.9 Reporting of Pregnancy

Pregnancy occurring during the study is not an adverse event, but it should be brought to the attention of the sponsor as soon as possible. The continuation of a subject who becomes pregnant will be determined on a case by case basis.

9 STATISTICAL CONSIDERATIONS

9.1 Statistical Hypotheses

• Primary Efficacy Endpoint(s):

The primary efficacy endpoint is time in weeks from baseline to the initial observation closure of a complete wound healing, over 26 weeks, that is confirmed at two consecutive visits each two weeks apart. The primary efficacy endpoint will be analyzed using the Cox regression analysis (i.e., proportional hazards model) to assess the effect of TTAX01 treatment on time to complete wound healing compared to SC in terms of hazard ratio and difference in the curve of the proportion of subjects reaching the complete wound healing over the 26-week treatment period.

The null hypothesis is that the hazard ratio of TTAX01 arm vs, SC arm is not statistically different from 1.0. The alternative hypothesis is that the hazard ratio is lower than 1.0 at the significance level of <0.05.

• Secondary Efficacy Endpoint(s):

Secondary efficacy endpoints in this study include proportions of index ulcers healed by Week 50, proportions of wound re-ulcerations by Week 50, proportions of minor and major amputations by Week 50, and total score of PROMIS Lower Extremity Function Questionnaire at end of study.

For index ulcer healing by Week 50, the null hypothesis is that the proportion of subjects with wound healing will not be statistically different between the two treatment arms of this study at Week 50. The alternative hypothesis is that a greater proportion of subjects in the SC plus TTAX01 arm will have index ulcers healed at Week 50, compared to the SC alone arm.

For index ulcer re-ulceration by Week 50, the null hypothesis is that, among those subjects who have had the index ulcer healed before Week 50, the proportion of subjects with wound re-ulcerated will not be statistically different between the two treatment arms of this study at

Week 50. The alternative hypothesis is that a smaller proportion of subjects in the SC plus TTAX01 arm will have index ulcers re-ulcerated at Week 50, compared to the SC alone arm.

For minor and major amputations by Week 50 following initial procedure, the null hypothesis is that the proportion of subjects receiving minor and/or major amputations will not be statistically different between the two treatment arms of this study by Week 50. The alternative hypothesis is that a smaller proportion of subjects in the SC plus TTAX01 arm will have minor and/or major amputations by Week 50, compared to the SC alone arm.

For total score of CWIS and PROMIS Questionnaires, the null hypothesis is that a total score (or better quality-of-life) of this measure will not be statistically different between the two treatment arms of this study at the end of study. The alternative hypothesis is that a greater total score (or better quality-of-life) of one or both of these measures will be seen for the SC plus TTAX01 arm at the end of study, compared to the SC alone arm.

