1.1 Study Synopsis

1.1 Study Sy	nopsis
Title:	A Multicenter Phase 3 Trial of Biotherapy using Cryopreserved Human Umbilical Cord (TTAX01) for Late Stage, Complex Non-healing Diabetic Foot Ulcers (AMBULATE DFU)
Study Description:	It is hypothesized that application at 4-week or greater intervals of the human placental umbilical cord tissue TTAX01 to the surface of a well debrided, complex diabetic foot ulcer (DFU) will, with concomitant management of infection, will result in a higher rate of wounds showing complete healing within 26 weeks of initiating therapy, compared with standard care alone. This confirmatory Phase 3 study examines a population of diabetic foot ulcer patients having adequate perfusion, with or without neuropathy, and a high suspicion of associated osteomyelitis in a complex, high grade wound.
Objectives:	Primary Objective: To determine whether treatment of high grade DFU with standard care plus TTAX01 results in a higher probability of achieving complete wound closure over 26 weeks, compared with standard care alone. Secondary Objectives: To compare differences between treatment groups in proportions of wounds healed through 50 weeks, long term durability of closure, limb preservation, and patient reported mobility (lower extremity function) at study end.
Endpoints:	Primary Endpoint: Time from baseline to initial observation of healing, over 26 weeks, where healing has been confirmed at two consecutive visits each two weeks apart. Secondary Endpoints: Proportions of wounds healed by Week 50, proportions of re-ulcerations by Week 50, proportions of minor and major amputations by Week 50, total score on a lower extremity function quality
Study Population:	of life measure. A total of 250 adult subjects aged ≥18 year-old with reasonably controlled diabetes mellitus and a complex non-healing DFU with high risk factors of [1] ulcer depth indicating exposed bone, tendon, muscle, and/or joint capsule and [2] clinical suspicion of osteomyelitis.
Phase:	3

Description of Sites/Facilities Enrolling Participants:	Approximately 20 United States and 3 Taiwanese sites specializing in care of diabetic foot ulcers, including hospital or outpatient based wound practices such as podiatric office practices, wound care centers, dermatology and vascular surgery clinics. Each site will have access to inpatient or outpatient surgery facilities for the accomplishment of initial surgical debridement.

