9.2 Sample Size Determination

The sample size for this trial was estimated using CreoStat HB StudySize software, v3.0.2. Using a log rank, two-sided, non-parametric Proportional Hazards (Freedman) approach, with accrual time assumed to be zero, α set to 0.025, 1- β set to 0.90, wound "survival" in the control arm set to 60% (thus 40% healed), and wound "survival" in the TTAX01 arm set to 35% (thus 65% healed), assuming 1:1 randomization and a 10% dropout, it is estimated that 94 subjects per group will be needed. As an added margin, 110 will be enrolled per group in the US portion of the trial (increases power to 94%). Three additional sites in Taiwan are expected to participate in this multicenter trial, but consistency of data between the US and TW sites is unknown. Therefore, the TW sites will be allowed to enroll 10 subjects per site, for an additional 30 subjects overall (15 per arm). This raises the power to 97%, assuming all data are acceptable for analysis.

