9.4.2 Analysis of the Primary Efficacy Endpoint

The primary efficacy endpoint of time in weeks from baseline to the initial observation closure of a complete wound healing, over 26 weeks, confirmed at two consecutive visits each two weeks apart will be analyzed using the Cox regression analysis (i.e., proportional hazards model) to assess the effect of TTAX01 treatment on time to complete wound healing compared to SC in terms of hazard ratio and difference in the curve of the proportion of subjects reaching the complete wound healing over the 26-week treatment period. For those subjects who discontinue from the treatment period prematurely without wound closure data collected over the confirmation period, those subjects who have missing data of wound closure over the confirmatory period and those subjects whose index ulcers are not deemed to be completely closed at the end of the 26-week treatment period, the time to the closure of a complete wound healing will be considered being censored at the corresponding time point.

The Cox regression model will include the treatment as the main predictor, whereas the subject's baseline index ulcer size and duration will be included in the model as covariates to adjust potential effects on time to wound closure. SAS PROC PHREG will be used to conduct the Cox regression analysis. The estimated hazard ratio of SC plus TTAX01 arm vs, SC alone arm and its 95% confidence intervals (CI) for wound healing will be reported.

For summary statistics and graphic illustrations of the primary efficacy endpoint, the obtained proportion of subjects with complete wound healing, the estimated median of time in weeks to the complete wound healing and the 95% CI as well as the estimated probabilities at each of

the 26 weeks of index ulcer non-closure will be analyzed and reported for each of the two treatment arms, using the method of Kaplan-Meier survival analysis with SAS PROC LIFETEST.

The analysis of the primary efficacy endpoint will be performed for the ITT population and PP population.

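### The primary alternative hypothesis is written as a hazard ratio below 1.0, which for a healing event means slower healing on TTAX01

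*Protocol*

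**What the plan says.** - **Event.** Section 9.1 uses Cox regression "to assess the effect of TTAX01 treatment on time to complete wound healing compared to SC in terms of hazard ratio". Section 9.4.2 says that for subjects without confirmed closure "the time to the closure of a complete wound healing will be considered being censored at the corresponding time point". Healing is therefore the event, and wounds that stay open are censored.
- **Orientation.** Section 9.1: "The null hypothesis is that the hazard ratio of TTAX01 arm vs, SC arm is not statistically different from 1.0". Section 9.4.2 reports "The estimated hazard ratio of SC plus TTAX01 arm vs, SC alone arm and its 95% confidence intervals (CI) for wound healing". TTAX01 is the numerator in both places.
- **Alternative.** Section 9.1: "The alternative hypothesis is that the hazard ratio is lower than 1.0 at the significance level of <0.05".
- **Aim.** The primary objective (section 1.1, repeated in section 3) is to show that adding TTAX01 "results in a higher probability of achieving complete wound closure over 26 weeks".
- **Planning assumption.** Section 9.2 assumes 40% healed on control and 65% on TTAX01.
- **Test level.** Section 9.4.1 sets two-sided 5% tests unless stated otherwise.

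**The concern.** In most survival analyses the event is bad and a hazard ratio below 1 is the benefit. Here the event is healing, so a ratio of TTAX01 to SC below 1 means that wounds on TTAX01 close more slowly. The alternative appears to have kept the usual survival convention although the event is favourable.

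Taken literally, significantly slower healing on TTAX01 would support the stated alternative, and the benefit the trial is designed to show would fall outside it. The sentence is the primary hypothesis of an open-label Phase 3 confirmatory trial, so readers should not have to infer its direction against its own wording. If it is corrected only after open-label data have accumulated, questions will follow about when the direction was fixed.

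There are two smaller faults in the same sentences. The alternative is one-directional and carries its own 0.05 level, whereas section 9.4.1 sets two-sided tests. The null describes the outcome of a significance test instead of giving the parameter a value.

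**Working it through.** **1. Does any section rescue the wording?** A ratio below 1 would mean benefit only if the ratio were SC over TTAX01, or if the event were something other than healing.

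- Orientation: TTAX01 over SC in both 9.1 and 9.4.2. No section inverts it.
- Event: healing in both. Section 9.2 describes unhealed wounds as surviving, but leaving that state is healing, so the hazard is still the healing hazard.
- House style: each secondary alternative in 9.1 is worded in the direction of TTAX01 benefit (more healed, fewer re-ulcerated, fewer amputations, better scores). Only the primary is reversed.

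**2. Reproducing the plan's sample size.** Inputs from section 9.2: 60% and 35% unhealed, Freedman log-rank, power 0.90, 1:1 allocation, 10% dropout.

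- Hazard ratio of healing, TTAX01 versus SC: ln(0.35)/ln(0.60) = 1.0498/0.5108 = 2.055.
- Freedman events at 0.025 per tail: (1.960 + 1.282)² × [(1 + 2.055)/(1 − 2.055)]² ≈ 88.1, rounded up to 89.
- Mean proportion healed: (0.40 + 0.65)/2 = 0.525.
- Per arm before dropout: 89/0.525/2 = 84.8.
- With dropout: 84.8/0.9 = 94.2, or 84.8 × 1.1 = 93.2.

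This agrees with the stated 94 per group. By the same method, power is 94.1% at 110 per arm and 96.4% at 125 per arm, against the stated 94% and 97%. The design was therefore built on a healing hazard ratio of about 2.06 or its reciprocal, 0.487. Freedman's formula gives 89 events for either, so the sample size does not reveal or depend on the direction. The value 0.487 arises only as SC over TTAX01, which the protocol never uses.

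**3. How the written alternative behaves under the planned effect.** The log hazard ratio is ln(2.055) = 0.720, and its standard error is approximately 2/√events.

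| Per arm | Events = 2n × 0.9 × 0.525 | SE | P(estimated HR < 1) | P(significant, HR < 1) | P(significant, HR > 1) |
|---|---|---|---|---|---|
| 110 | 104.0 | 0.196 | Φ(−3.67) ≈ 0.0001 | ≈ 1 × 10⁻⁸ | 95.7% |
| 125 | 118.1 | 0.184 | Φ(−3.91) ≈ 0.00005 | ≈ 2 × 10⁻⁹ | 97.5% |

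Significance here is two-sided 0.05. A simulation of 1,000 trials (110 per arm, exponential healing times, 26 weeks, no dropout) gave a median hazard ratio of 2.09. In 96.9% of trials the result was significant with HR > 1, and in none was it significant with HR < 1.

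**4. Error level.** The stated 94 is reproduced with 0.025 per tail, that is, two-sided 0.05. Section 9.2, however, describes a two-sided method with α of 0.025. Taken literally, that needs 105 Freedman events, or 100 per arm before dropout and 110 to 111 after it. If section 9.1 is read as a one-sided test at 0.05, the per-tail error is twice what the sample size used.

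**The case against.** The strongest reply is that nothing in the analysis turns on the word that is wrong. Section 9.4.1 calls for superiority comparisons at two-sided 5%, section 9.4.2 specifies the Cox model with its ratio and 95% interval, and no interim analysis is planned. The p-value, interval, sample size and conduct are the same whichever direction section 9.1 names. The objective and the 65% versus 40% assumption make the intent plain, and no one reading the whole protocol would claim success on slower healing. All of this stands, and it limits the numerical harm.

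The smaller faults are also open to reply. A directional hypothesis tested two-sided is common drafting, the secondary alternatives are written the same way, and section 9.4.1 settles the sidedness. The null wording is loose, but it does name 1.0. Both would be minor on their own. They are worth repairing because they sit in the sentences that have to be rewritten anyway.

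The small probabilities measure no loss of power and no inflation of type I error. They show only that the written alternative excludes essentially the whole planned effect. The figure for 125 per arm also depends on the Taiwan data being acceptable, which section 9.2 leaves open, so the figure for 110 is given beside it.

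None of this makes the sentence correct. Section 9.4.2 does not say which side of 1 is benefit, so nothing later in the protocol puts it right.

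**Conclusion.** The point holds. With healing as the event and TTAX01 as the numerator, the primary alternative in section 9.1 names the direction of harm. It conflicts with the primary objective, with the planned 65% versus 40% healed (hazard ratio 2.06), and with the direction of every secondary alternative. Under the planned effect, an estimate on the stated side of 1 has a probability of about 0.0001 at 110 per arm and 0.00005 at 125 per arm. These figures assume proportional hazards, 10% dropout and the usual approximation for the standard error. The direction of the error depends on none of these assumptions.

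The two-sided analysis and the sample size are unaffected. The fault lies in the written decision rule. Because this is the primary hypothesis of a confirmatory trial and the correction costs almost nothing, it must be fixed.

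**What to change.** Rewrite the primary hypothesis in section 9.1 along these lines:

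- H0: HR = 1, where HR is the hazard of confirmed healing on TTAX01 plus SC relative to SC alone.
- H1: HR ≠ 1, tested at two-sided α = 0.05, consistent with section 9.4.1.
- Success requires p < 0.05 with an estimated HR above 1.
- A ratio above 1 means faster healing on TTAX01. Add the same statement to section 9.4.2.

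Changing the direction word alone would cure the main error. Inverting the ratio to SC over TTAX01 would also do so, provided that 9.1 and 9.4.2 are changed together. The fuller rewrite is preferable because it settles direction, sidedness and the form of the null at once.

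In the same edit, align the α statement in section 9.2 with the level that gives 94 per group: two-sided 0.05, equivalently 0.025 per tail.

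The cost is a few sentences in a protocol amendment, with matching text in the SAP. Sample size, data collection and trial conduct do not change. The correction should be made and dated before any comparison of outcomes by arm.

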3 OBJECTIVES AND ENDPOINTS

OBJECTIVES	ENDPOINTS	JUSTIFICATION FOR ENDPOINTS			
Primary					
To determine whether treatment of high grade DFU with standard care plus TTAX01 results in a higher probability of achieving complete wound closure over 26 weeks, compared with standard care alone.	Time from baseline to initial observation of healing, over 26 weeks, where healing has been confirmed at two consecutive visits each two weeks apart.	The endpoint complies with FDA guidance. Dropouts should be minimal during the first 26 weeks, but may increase thereafter. Analysis will use a Cox proportional hazard model			
Secondary					
To compare differences between treatment groups in proportions of wounds healed through 50 weeks	Proportions of wounds healed by Week 50	This endpoint provides insight into longer term benefits of the intervention			
To compare long term durability of closure between treatment groups	Proportions of wounds that re-ulcerate by Week 50	May provide insight into the quality of healing			
To compare limb preservation between treatment groups	Proportions of minor (portions of the foot) and major (ankle, above or below the knee) amputations following the initial procedure by Week 50	Each amputation risks loss of mobility, with consequent increased mortality			
To compare patient reported mobility (lower extremity function) between groups.	Total score on PROMIS Health Organization Neuro- QoL "Lower Extremity Function" at Study End.	The tool is an NIH validated measure of patient reported outcomes			
Safety					
To examine Quality of Life endpoints related to therapeutic intervention	Total score of quality of life assessment determined by Cardiff Wound Impact Schedule (CWIS) at Study End				
Proportion of subjects experiencing adverse events, by group	Spontaneously reported and elicited adverse events, coded in MedDRA				

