9.4.3 Analysis of the Secondary Endpoints

Secondary efficacy endpoints in this study include proportions of index ulcer healed by Week 50, proportions of wound re-ulcerations by Week 50, proportions of minor and major amputations by Week 50, and total score of PROMIS Lower Extremity Function Questionnaire at end of study.

The non-parametric Cochran-Mantel-Haenszel (CMH) test with adjustment for baseline wound size cohort will be used to examine treatment effects for the SC plus TTAX01 arm vs. SC alone arm on proportion of subjects with index ulcer achieving and remaining healed at Week 50, proportion of subjects (among those with complete wound healing before Week 50) with wound re-ulceration at Week 50, and proportion of subjects with minor and/or major amputations by Week 50. Subjects' missing values at Week 50 in these endpoints, due to either no assessment or early termination from the study, will be imputed using the last-observation carry forward (LOCF).

An analysis of covariance model (ANCOVA) with treatment and baseline wound size as effect will be used to analyze total score of PROMIS Lower Extremity Function Questionnaire at end of study. Subjects' missing values in this endpoint, due to either no assessment or early termination from the study, will utilize the assessment collected at the early termination visit.

The analyses of the secondary efficacy endpoints will be performed for the ITT population and PP population as well as the LO population.

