9.4.4 Safety Analyses

Safety measures will be reported as summary statistics during treatment, with shift tables provided for laboratory measures taken at baseline and end of study. Adverse events will be coded using the version of MedDRA available at the start of the trial. Each AE will be counted once for each subject unless it resolves and recurs, in which case it may appear as multiple AEs. Severity, frequency, and relationship of AEs to study intervention will be presented by System Organ Class (SOC) and preferred term groupings.

Listings will be provided for discontinuations, deviations, compliance, AEs leading to discontinuation, and AEs related to the index ulcer. AE listings will include severity and relationship to test article, as well as actions taken.

Tables will be provided summarizing reasons for screen failure, reasons for premature discontinuation, protocol deviations, subject compliance, treatment emergent AEs (TEAEs), TEAEs of interest, TEAEs by severity, SAEs, and AEs leading to discontinuation as well as total score of Cardiff Wound Impact Schedule (CWIS).

Where applicable, analyses of safety measures will be conducted, respectively, for the 26-week treatment period of the safety population and for the long-term observation period of the LO population. Missing values in safety measures will remain as missing in analyses.

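### Section 9.1 states a secondary efficacy hypothesis that a better score on either PROMIS or CWIS would satisfy, although the rest of the protocol makes PROMIS the only patient-reported secondary efficacy endpoint and treats CWIS as a safety measure

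*Protocol*

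**What the plan says.** Section 9.1 lists the secondary efficacy endpoints and ends the list with PROMIS as the only patient-reported item: "and total score of PROMIS Lower Extremity Function Questionnaire at end of study". Under the same heading it then states a hypothesis for two instruments. The null begins "For total score of CWIS and PROMIS Questionnaires, the null hypothesis is that a total score (or better quality-of-life) of this measure", and the alternative is that "a greater total score (or better quality-of-life) of one or both of these measures will be seen for the SC plus TTAX01 arm".

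Section 3 keeps the instruments apart. The secondary objective "To compare patient reported mobility (lower extremity function) between groups" is paired with the PROMIS/Neuro-QoL Lower Extremity Function total score. Under the Safety heading, the objective "To examine Quality of Life endpoints related to therapeutic intervention" is paired with "Total score of quality of life assessment determined by Cardiff Wound Impact Schedule (CWIS) at Study End". The synopsis in Section 1.1 also has a single patient-reported secondary endpoint, a lower extremity function measure.

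Section 9.4.3 plans an ANCOVA with treatment and baseline wound size for the "total score of PROMIS Lower Extremity Function Questionnaire at end of study". It gives no analysis of CWIS. Section 9.4.4 puts the CWIS total score among the safety tables, says safety measures are reported as summary statistics, and leaves missing safety values missing.

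**The concern.** A hypothesis filed under secondary efficacy should concern a secondary efficacy endpoint. This one adds a second instrument that the protocol classes as safety and can be satisfied by that instrument alone. Its two halves then differ in endpoint class, analysis population, missing-data rule and method.

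Two things are at stake. It is unclear in advance which instrument carries the patient-reported result, in a confirmatory trial where treatment is not blinded (Sections 2.1 and 6.3). An either-or rule with no split of the significance level also gives the hypothesis two chances of a false positive.

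**Working it through.** **Step 1: how the protocol treats each instrument.**

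| Feature | PROMIS | CWIS |
|---|---|---|
| Section 3 class | Secondary | Safety |
| In the 9.1 list of secondary efficacy endpoints | Yes | No |
| In the 9.1 joint hypothesis | Yes | Yes |
| Named method | ANCOVA (9.4.3) | None of its own; safety table (9.4.4) |
| Missing values | Early-termination assessment used (9.4.3) | Left missing (9.4.4) |
| Population | ITT, PP and long-term observation (9.4.3) | Safety and long-term observation, where applicable (9.3, 9.4.4) |

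The joint hypothesis is the only place where CWIS appears on the efficacy side. Its null is also singular (one measure), while its alternative covers one or both, so the two do not match.

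**Step 2: what the literal wording allows.** Suppose PROMIS shows no difference and CWIS is better in the TTAX01 arm. One of the two measures is better, so the alternative is satisfied.

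**Step 3: error rate of the either-or reading.** The protocol states no error rate or power for this hypothesis, so there is no figure to reproduce.

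Inputs:
- Level: 5% two-sided per test (Section 9.4.1), with no split between instruments. That is 2.5% in the TTAX01-favouring direction, critical value c = 1.96.
- Correlation ρ between the two test statistics under no effect: not given. Assumed values 0, 0.5 and 0.9.

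Formulas:
- Favouring TTAX01, independent: 1 − (1 − 0.025)² = 1 − 0.950625 = 0.0494.
- Favouring TTAX01, correlated: 1 − Φ₂(c, c; ρ), where Φ₂ is the bivariate normal distribution function.
- Either direction, independent: 1 − (1 − 0.05)² = 1 − 0.9025 = 0.0975.
- Either direction, correlated: 1 − [Φ₂(c, c; ρ) − 2Φ₂(−c, c; ρ) + Φ₂(−c, −c; ρ)].

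| ρ (assumed) | False result favouring TTAX01 | Ratio to 2.5% | False result in either direction |
|---|---|---|---|
| 0 | 4.94% | 1.98 | 9.75% |
| 0.5 | 4.54% | 1.82 | 9.07% |
| 0.9 | 3.52% | 1.41 | 7.04% |
| PROMIS alone | 2.5% | 1.00 | 5% |

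The first result column answers the hypothesis as written, because its alternative is directional. The last column includes results favouring standard care, which could not satisfy it.

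**The case against.** Four points deserve a fair hearing.

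- **The mobility objective.** A reader might infer that a CWIS result could be used to declare the mobility objective met. The protocol does not say so. Section 3 pairs that objective with PROMIS alone, Section 9.4.3 analyses PROMIS alone, and the 9.1 hypothesis speaks of quality of life. This objection stands, and the point does not rest on a mobility claim.
- **No test for CWIS.** A reader might infer that CWIS would never be compared between arms. Section 9.4.1 says all data will be analysed for superiority comparisons and leaves detailed methods to the SAP, which is not at hand. What can be said is only that the protocol names no CWIS-specific method. The absence of a model is not the defect. The hypothesis and the endpoint classes are fixed in the protocol, and they conflict there. An SAP that added a CWIS test without changing 9.1 would put the two-chance rule into effect.
- **Loose wording rather than a decision rule.** The singular null fits one comparison per instrument, and 9.1 sets no explicit success criterion. That reading is possible, so the error rates apply to the literal either-or reading. The classification conflict stands on both readings.
- **Size.** A doubling of the error rate is tempting to quote, but the ratio is close to two only at low correlation. Both questionnaires contain mobility items (Appendix 12.2 and 12.3), so independence is the least plausible case. At correlation 0.9 the ratio is about 1.4.

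**Conclusion.** The inconsistency is real and lies within the protocol. Section 9.1 states a secondary efficacy hypothesis that CWIS alone could satisfy. That conflicts with Sections 1.1, 3 and 9.4.3 and with 9.1's own endpoint list on the status of PROMIS, and with Sections 3 and 9.4.4 on the status of CWIS.

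On the either-or reading, the one-directional false-positive rate is 3.5% to 4.9%, against 2.5% for PROMIS alone. This assumes both instruments are tested at two-sided 5% without adjustment and that the correlation lies between 0 and 0.9. The primary endpoint, its significance level and the sample size are not touched. The change should be made, but its reach is limited to one secondary hypothesis.

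**What to change.** In Section 9.1, limit the patient-reported hypothesis to the PROMIS total score. Remove CWIS from the null and the either-or phrase from the alternative. This matches Sections 1.1, 3 and 9.4.3. Keep CWIS in Section 9.4.4 as a descriptive measure, with by-arm means and a 95% confidence interval and no success claim.

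The protocol does not show which role the sponsor intended for CWIS. If a CWIS claim is wanted, list it as a secondary endpoint in Sections 3, 9.1 and 9.4.3, with its own hypothesis, model, population and missing-data rule, and a multiplicity rule. For example, testing each instrument at two-sided 2.5% (Bonferroni) holds the pair to at most 2 × 2.5% = 5%.

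The first option costs an edit to the hypothesis wording in 9.1 and a line in 9.4.4, and gives up a stand-alone CWIS claim. The second costs edits in three sections and a stricter level for PROMIS if the level is split.
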